### 3.4 Sample requirements

#### 3.4.1 Sample collection

- 1) Test performance evaluation: 20 mL of peripheral venous blood is needed for the testing with test reagent and control method (note: 10 mL/tube, in total of two tubes). Transfer the blood into a disposable vacuum blood collection tube, mix the blood and anticoagulant by gently inverting the tube 5~6 times.
- 2) Diagnostic performance evaluation: 10 mL of peripheral venous blood is needed (note: 10 mL/tube). Transfer the blood into a disposable vacuum blood collection tube, mix the blood and anticoagulant by gently inverting the tube 5~6 times.

#### 3.4.2 DNA extraction and sample testing

Samples are processed in strict accordance with standard operating procedures. After nucleic acid extraction, samples should be tested with the test reagent and control method according to the instructions for use, and the raw data should be kept at the same time.

#### 3.4.3 Storage and transportation

Blood samples in disposable blood collection tubes should be stored at 6~37°C for no more than 7 days.

The separated plasma samples should be subject for extraction immediately. If the samples cannot be processed immediately, they should be stored in a  $-20\pm5^{\circ}\text{C}$  refrigerator for no more than 6 months.

The extracted cfDNA should be stored at  $-20\pm5^{\circ}\text{C}$  for no more than 6 months. The extracted cfDNA should be transported upon dry ice and the transportation period should not be more than 110 hours.

### **3.5 Trial Implementation Process**

#### **3.5.1 Number of included samples**

The included samples are numbered before testing, and the numbers are recorded in Screening Inclusion Form. Each clinical trial center will appoint a designated person responsible for numbering the sample that meet the inclusion criteria.

Principle of sample numbering:

[figure not shown]
Each sample has a 1 letter (A/B, group number) plus a unique 5-digit number.

A represents the group for performance evaluation of test reagent, and B represents the group for percent agreement evaluation of test reagent.

The 1st digit of the number represents the code of the clinical trial center, and the 2nd to 5th digits represent the sequence of inclusion:

For example: the first included sample from the Third Affiliated Hospital of Sun Yat-sen University in the group for performance evaluation: A10001.

A 1 0001

The code of the clinical trial center

Inclusion sequence number

Test group number

#### **3.5.2 Blinding**

In principle, one subject only provides one sample, and each subject should have a unique clinical trial number (secondary code). After the samples are included and before the test implementation, the blinding personnel should stick the secondary number on the tube, and save the mapping table of the secondary number and primary number (the

unique traceable number of the subject). Before sample testing, the Blindness Record should be developed by an investigator and reviewed by another investigator for both of them who do not participate in sample testing, then retained by the blinding personnel independently. During the test, only the secondary code of the sample is knowable.

### 3.5.3 Unblinding

After the samples are tested with the test reagent and control method, the results are unblinded.

## 3.6 Duration of Clinical Trial

This clinical trial went through protocol drafting, project establishment, ethics review, agreement signing, human genetic resources approval, registration and back-up, clinical initiation and pre-test, enrollment, completion of enrollment, statistical analysis, completion of report, and seal, the duration is about 18 ~ 36 months. If the sample collection is smooth and the number of samples meets the test requirements, the duration clinical trial can be shortened; if it is not smooth, the duration can be appropriately extended.

## 3.7 Statistical Method of Clinical Trial

### 3.7.1 Principles of statistical analysis

SAS9.4 software (or higher version) is used for statistical analysis, and PASS16 software (or higher version) is used for sample size calculation. All statistical tests are two-sided (unless otherwise stated).

Basic principles of statistical description: The quantitative data (such as age, gender, etc.) are expressed in forms of mean, standard deviation, median, minimum value, maximum value, lower quartile (Q1), and upper quartile (Q3) according to the distribution of the data; the qualitative data are expressed in forms of the number of cases and the corresponding proportion.

### 3.7.2 Analysis of general data

The basic demographics and information (such as age, gender and medical history, cancer stage, etc.) of the included cases are statistically described. The quantitative data

are expressed in forms of mean, standard deviation, median, minimum value, maximum value, lower quartile (Q1), upper quartile (Q3); categorical data are expressed in forms of the number of cases and the proportion.

### 3.7.3 Statistical evaluation of test performance

Evaluation indicators: positive percent agreement, negative percent agreement and overall percent agreement, and the corresponding 95% confidence interval.

A four-fold table is used to calculate the positive percent agreement, negative percent agreement, positive predictive value, negative predictive value, overall percent agreement and 95% confidence interval of the test reagent and the control method.

Table 1 Statistics of clinical results of test reagent and control method

Test product	Control method		Total
	Positive	Negative	
Positive	A	B	A+B
Negative	C	D	C+D
Total	A+C	B+D	A+B+C+D

Note: A sample with a mutation genotype is judged as positive, and a sample with no mutation genotype is judged as negative.

The calculation formula of the percent agreement is as follows:

$$\text{Positive percent agreement} = A/(A+C) \times 100\%$$

$$\text{Negative percent agreement} = D/(B+D) \times 100\%$$

$$\text{Overall percent agreement} = (A+D)/(A+B+C+D) \times 100\%$$

The calculation formula of 95% confidence interval:  $p \pm 1.96 \times [p(1-p)/n]^{1/2}$  (where p is the positive percent agreement, negative percent agreement, and overall percent agreement, n is the sample size. If  $p > 0.9$ , use Wilson score method for correction).

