## 3.2 Test performance evaluation

### 3.2.1 Test performance evaluation method

Following the principle of concurrent blinding, the blood samples are collected from the non-HCC patients and patients with liver cancer who had been diagnosed according to the clinical diagnostic criteria for primary liver cancer. The clinical diagnosis of primary liver cancer is determined in accordance with the clinical diagnostic criteria in Guidelines for diagnosis and treatment of primary liver cancer (2019 Edition) set by the National Health Commission. The enrolled subjects are coded. The selected samples are tested with test reagent and the control method high-throughput human methylation sequencing (NGS sequencing method), the test results are compared.

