### 3.2.2 Determination of the sample size for test performance evaluation

According to the pre-clinical independent cohort verification results of 6 liver cancer-specific methylation sites that were screened out, the number of positive samples should be not less than 78; the number of negative samples should be not less than 238; the samples available in this study should be not less than 316 cases.

Considering that the mutation rate of some genes is extremely low (AK055957, DAB2IP, TBX15, GRASP, PPFIA1, PSD4), the subjects should be enrolled sequentially, and at least one positive case should be screened out in each type of gene mutation. If the requirements are not met, more subjects should be enrolled for testing. It should be ensured that all samples are traceable.

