### 3.2.3 Inclusion Criteria

- 1) Confirmed primary hepatocellular carcinoma or confirmed non-HCC;
- 2) I or my legal representative can read, understand and sign the informed consent;
- 3) Agree to provide blood samples and have good clinical compliance;
- 4) The basic clinical information is complete, including: the patient's unique traceability number (ID number/outpatient clinic number/medical insurance card number), age, gender, imaging and/or pathological diagnosis results (for patients with primary liver

cancer), imaging examination confirmed non-identical Liver cancer (non-HCC patients).

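### Section 3.7.3 calls for PPV and NPV from the reagent-versus-NGS table, where they depend on the recruitment mix and are not predictive values for liver cancer

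*Protocol*

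**What the plan says.** **How the sample is formed.** Under Protocol section 3.2.1, "the blood samples are collected from the non-HCC patients and patients with liver cancer who had been diagnosed". The first inclusion criterion in section 3.2.3 is "Confirmed primary hepatocellular carcinoma or confirmed non-HCC". Section 3.2.2 sets minimum counts: "the number of positive samples should be not less than 78", "the number of negative samples should be not less than 238" and "the samples available in this study should be not less than 316 cases". It also asks for at least one positive case for each gene, and adds: "If the requirements are not met, more subjects should be enrolled for testing". No upper limit is given.

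**What the reference is.** Section 3.2.1 names high-throughput methylation sequencing (NGS) as the control method. Table 1 in section 3.7.3 crosses the reagent result with the control-method result.

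**What is to be calculated.** Section 3.7.3 opens with: "Evaluation indicators: positive percent agreement, negative percent agreement and overall percent agreement, and the corresponding 95% confidence interval". The next sentence widens the list to include "positive predictive value, negative predictive value, overall percent agreement and 95% confidence interval of the test reagent and the control method". The formulas that follow cover positive percent agreement (PPA), negative percent agreement (NPA) and overall agreement only. The confidence-interval definition limits p to the same three.

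**Where disease predictive values appear.** Section 3.7.4 defines PPV and NPV against clinical diagnosis, with formulas, and includes them in its confidence-interval definition. They apply to the high-risk subjects of section 3.3, planned at no fewer than 4500.

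**The concern.** PPA and NPA condition on the reference result, so the ratio of reference-positives to reference-negatives does not enter their formulas. PPV and NPV condition on the reagent result, so that ratio enters directly. A sample recruited by known disease status has a ratio that recruitment produces. It estimates no population's prevalence.

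The reference adds a second difficulty. In Table 1, A/(A+B) is the share of reagent-positives that sequencing confirms. It is not the probability of liver cancer given a positive reagent result, which is how the name will be read, particularly when section 3.7.4 uses the same name for that probability.

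Followed as written, the report would carry two quantities under one label, one of them governed by how many subjects of each kind were recruited. A reader could take the section 3.7.3 figure for the reagent's predictive value in screening.

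**Working it through.** **1. The plan's own figure.** 78 + 238 = 316, which matches the stated minimum total. At the minima the positive share is 78/316 = 24.7%.

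**2. What is assumed.** The protocol gives no expected PPA or NPA and no prevalence in the intended-use population, so all three are assumptions here. Section 3.2.2 does not say whether a positive sample means an HCC patient or an NGS-positive sample. The 24.7% applies to Table 1 only if it means NGS-positive, so it is an assumption too.

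**3. Formulas.** With s = PPA, c = NPA and π = share of reference-positives:

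- PPV = sπ / [sπ + (1−c)(1−π)]
- NPV = c(1−π) / [c(1−π) + (1−s)π]

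**4. At the minima, s = c = 95%.** The expected cells are A = 0.95 × 78 = 74.1, C = 3.9, B = 0.05 × 238 = 11.9 and D = 226.1.

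- PPV = 74.1 / (74.1 + 11.9) = 86.2%
- NPV = 226.1 / (226.1 + 3.9) = 98.3%

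**5. Same agreement, 5% positive.**

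- PPV = 0.0475 / (0.0475 + 0.0475) = 50.0%
- NPV = 0.9025 / (0.9025 + 0.0025) = 99.7%

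**6. Range over the assumptions.**

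| Share positive | PPV / NPV at 95%/95% | PPV / NPV at 90%/90% |
|---|---|---|
| 1% | 16.1% / 99.9% | 8.3% / 99.9% |
| 5% | 50.0% / 99.7% | 32.1% / 99.4% |
| 10% | 67.9% / 99.4% | 50.0% / 98.8% |
| 24.7% (the minima) | 86.2% / 98.3% | 74.7% / 96.5% |
| 40% | 92.7% / 96.6% | 85.7% / 93.1% |

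Within each column the reagent's agreement with NGS is constant. Only the mix changes.

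**7. Drift within the rules.** The counts are floors, so twice the minimum number of positives (156) with 238 negatives would also comply. At 95%/95%, A = 148.2 and C = 7.8. PPV becomes 148.2 / (148.2 + 11.9) = 92.6% and NPV 226.1 / (226.1 + 7.8) = 96.7%. PPA and NPA stay at 95%.

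**8. Consistency inside section 3.7.3.** This check needs no assumption.

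| Element of section 3.7.3 | PPA, NPA, overall agreement | PPV, NPV |
|---|---|---|
| Evaluation indicators | yes | no |
| Calculation sentence | yes | yes |
| Formulas | yes | no |
| Confidence-interval definition | yes | no |

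PPV and NPV appear only in the calculation sentence. Section 3.7.4, by contrast, supports them in both its formulas and its interval definition.

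**The case against.** The strongest reply is that little depends on these two terms. No hypothesis, sample size or success criterion in the protocol uses PPV or NPV from section 3.7.3, they are not among that section's indicators, and the disease values are already provided for in section 3.7.4. This stands, and it is why the point is minor. It does not give the ordered figures a meaning.

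A reader might infer three stronger things that the documents do not support:

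- **That 78:238 is a fixed quota.** The counts are minima, and further enrolment is allowed when a gene lacks a positive, so the ratio can move. What holds is that recruitment determines it.
- **That the section 3.7.3 PPV will overstate PPV in use.** This needs a positive share in use below the sampled share. That is plausible for at-risk people not selected by diagnosis, but the protocol states no prevalence. Above the sampled share the direction reverses. Where PPV is overstated, NPV is understated. Moreover, the relevant share for Table 1 is that of NGS-positives, not of liver cancers.
- **That the values of sections 3.7.3 and 3.7.4 would conflict.** They have different references and different populations, so different values are to be expected. The risk is misreading of a shared name.

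The section 3.7.4 values should not be overrated either. The wording of section 3.3.2 on how centres choose subjects leaves open how representative that cohort's prevalence will be. It is still the only part that has clinical diagnosis as the reference for this table and no minimum counts by disease status.

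Lastly, overall agreement is also a weighted average over the mix. It always lies between PPA and NPA, however, and section 3.7.3 lists it as an indicator, so the point does not extend to it.

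**Conclusion.** The point holds and is minor. The protocol's calculation sentence calls for PPV and NPV from a sample recruited by known status and judged against another assay. These values depend on the recruitment mix, are not predictive values for liver cancer in any population, and lack support in the section's own indicators, formulas and interval definition.

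The size can be shown only under assumptions. With 95% agreement on both sides, lowering the positive share from 24.7% to 5% takes PPV from 86.2% to 50.0% and NPV from 98.3% to 99.7%. The agreement rates, the 5% share, and the reading of the section 3.2.2 counts as NGS-positive and NGS-negative samples are all assumed. The dependence on the mix and the inconsistency inside section 3.7.3 do not rest on them.

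**What to change.** Delete positive and negative predictive value from the calculation sentence in section 3.7.3, so that it names PPA, NPA and overall agreement with their 95% confidence intervals, as the rest of the section does. Report PPV and NPV against clinical diagnosis only, from the high-risk cohort under section 3.7.4.

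If the sponsor wishes to keep the two proportions, the alternative is to rename them as sample-specific agreement with NGS, to state the mix they were obtained at, and to add formulas and an interval definition. Deletion is simpler and loses no planned conclusion.

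The cost is an edit to one sentence. No subjects, samples or data are affected. Under section 6 the revision must be recorded, agreed by the parties and re-approved by the ethics committee, so it can go in with the next amendment.

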### 3.7.4 Statistical evaluation of diagnostic performance

Table 2 Comparison of statistical results between the test reagent and clinical diagnostic standards

Test product	Clinical diagnostic criteria		Total
	Positive	Negative	
Positive	A (true positive)	B (false positive)	A+B

Negative	C (false negative)	D (true negative)	C+D
Total	A+C	B+D	A+B+C+D

The calculation formula of the sensitivity is as follows:

$$\text{Sensitivity} = A/(A+C) \times 100\%$$

$$\text{Specificity} = D/(B+D) \times 100\%$$

$$\text{Overall percent agreement} = (A+D)/(A+B+C+D) \times 100\%$$

$$\text{Positive predictive value (PPV)} = A/(A+B) \times 100\%$$

$$\text{Negative predictive value (NPV)} = D/(C+D) \times 100\%$$

The calculation formula of 95% confidence interval:  $p \pm 1.96 \times [p(1-p)/n]^{1/2}$  (where p is sensitivity, specificity, positive predictive value, negative predictive value, total percent agreement, n is the sample size. If  $p > 0.9$ , use Wilson score method for correction.)

At the same time, compare the diagnostic performance of test reagent + AFP, test reagent + AFP + US, AFP + US to the clinical diagnostic criteria.

### 3.7.5 Comparison of sensitivity across different test methods for screening liver cancer

Make statistical tests on the sensitivity superiority of test reagent + AFP to conventional method (AFP+US) for screening liver cancer, the sensitivity superiority of test reagent + AFP + US to conventional method for screening liver cancer, the sensitivity non-inferiority of test reagent + AFP + US to conventional method for screening liver cancer, the sensitivity non-inferiority of test reagent + AFP + US to conventional method for screening liver cancer.

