AFP in diagnosing liver cancer is about 60%, the false negative rate is 40%, the specificity is about 80%, and the false positive rate is 20%. For these reasons, AFP is no longer a screening indicator in AASLD guideline. For nodules larger than 2 cm, the sensitivity of US is still 84%; but for nodules of 0.5~2 cm in the liver, the sensitivity is only 33%. Therefore, there is an urgent need to find out a new biomarker for auxiliary diagnosis of liver cancer with higher sensitivity and specificity compared with current screening methods.

ctDNA, also known as Cell-free tumor DNA or circulating tumor DNA, circulates freely in the blood of patients with cancer. The analysis and comparison between ctDNA mutation and the site of normal genome by means of invasive approach can provide the useful information for tumor diagnosis, prognosis, and monitoring.

ctDNA generates from necrotic or apoptotic tumor cells, circulating tumor cells, and exosomes secreted by tumor cells. In the body of cancer patients, the number of ctDNA is small, the half life is short, and the size of ctDNA is about 160~180 bp. These fragments can reflect the number of tumor cells and its change. ctDNA is the "identity fingerprint" released by tumor cells into the blood, which is a tumor marker with high sensitivity and specificity . ctDNA is a non-invasive alternative for patients who are not suitable for tumor biopsy, which not only relieves the suffering, but also serves as an alternative to repeated invasive biopsy.

DNA methylation refers to the covalent bonding of a methyl group at the 5' carbon position of cytosine of genomic CpG dinucleotides under the action of DNA methyltransferases. DNA methylation is an important epigenetic mark information and one of the earliest discovered DNA modification pathways. It plays an important role in maintaining normal cell function, genetic imprinting, embryonic development and human tumorigenesis, and is also one of the popular topics of study. Alterations in DNA methylation level and pattern are an important factor in tumorigenesis. In normal cells, the CpG island located in the promoter region of tumor suppressor genes is in a low level or unmethylated state. At this time, tumor suppressor genes are in a normal open state, and the expression of tumor suppressor genes inhibits tumorigenesis. In tumor cells, the CpG

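### Section 3.7.5 compares the new strategies with AFP + US on sensitivity only; no paired comparison of specificity stands beside it

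*Protocol*

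**What the plan says.** The Background of the protocol (section 1) describes the need as a "new biomarker for auxiliary diagnosis of liver cancer with higher sensitivity and specificity compared with current screening methods".

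Section 3.7.4 defines sensitivity, specificity, PPV, NPV and overall agreement against the clinical diagnosis, with a 95% confidence interval for each ("where p is sensitivity, specificity, positive predictive value, negative predictive value, total percent agreement, n is the sample size"). It then asks the analyst to "compare the diagnostic performance of test reagent + AFP, test reagent + AFP + US, AFP + US to the clinical diagnostic criteria".

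Section 3.7.5, headed "Comparison of sensitivity across different test methods for screening liver cancer", holds the formal tests between strategies:

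- reagent + AFP: "Make statistical tests on the sensitivity superiority of test reagent + AFP to conventional method (AFP+US) for screening liver cancer";
- reagent + AFP + US: "the sensitivity superiority of test reagent + AFP + US to conventional method for screening liver cancer";
- reagent + AFP + US: "the sensitivity non-inferiority of test reagent + AFP + US to conventional method for screening liver cancer", an item that is printed twice.

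No item in 3.7.5 concerns specificity, false positives or PPV. Section 3.3.5 gives positivity rules for the reagent alone and for US + AFP, but none for either new combination. Section 3.3.1 has every subject in the diagnostic part undergo AFP, ultrasound, the reagent and contrast-enhanced MRI, so the design is fully paired.

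**The concern.** Adding a test to a combination usually buys sensitivity at the price of specificity. A formal comparison confined to sensitivity therefore credits extra positive results whether or not they carry information. The price falls on subjects without cancer, who are likely to be the large majority even of a high-risk cohort.

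The background names both properties as the need, yet only one enters a comparison between strategies. The separate specificity intervals in 3.7.4 do not use the fact that the same subjects receive all the tests, and 3.7.5 does not require them to be read together with a sensitivity result. A significant sensitivity result could thus be stated without the specificity change that produced it.

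**Working it through.** **1. What is compared, section by section.** Sensitivity is estimated per strategy in 3.7.4 and tested between strategies in 3.7.5. Specificity and PPV are estimated per strategy in 3.7.4, and no between-strategy comparison of them is specified. The only number behind the comparisons is the minimum of 4500 useful samples in 3.3.2. It comes without prevalence, expected rates, alpha or power, so it cannot be reproduced. It is not disputed here.

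**2. Assumptions for the illustration (none is in the protocol).** Either-positive rule for reagent + AFP + US; two-sided alpha of 0.05 (3.7.1 gives two-sided tests but no level); exact McNemar test; 45, 135 or 225 cancers among 4500 (1%, 3%, 5%); AFP + US sensitivity 60% and specificity 95%; a worthless reagent that is positive at random in 10% of subjects.

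**3. Direction.** Under the either-positive rule, every subject positive on AFP + US is also positive on reagent + AFP + US. All discordant pairs run one way. The sensitivity difference cannot be negative and the specificity difference cannot be positive, so non-inferiority on sensitivity is met by construction.

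**4. Threshold for superiority.** With k discordant cancers all in one direction, exact two-sided p = 2 × 0.5^k. For k = 5, p = 0.0625; for k = 6, p = 0.031. Six extra detected cancers are enough.

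**5. Chance that the worthless reagent reaches six.** The extra detections follow Binomial(missed cancers, 0.10):

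| Cancers | Missed by AFP + US | P(at least 6) |
|---|---|---|
| 225 | 90 (sensitivity 60%) | 0.897 |
| 225 | 112 (sensitivity about 50%) | 0.973 |
| 135 | 54 (60%) | 0.457 |
| 45 | 18 to 22 (60% to about 50%) | 0.006 to 0.018 |

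**6. What it costs in specificity.** With 225 cancers there are 4275 reference-negative subjects.

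- Combined specificity = 0.95 × 0.90 = 85.5%.
- Added false positives = 4275 × (0.95 − 0.855) = 406.
- Expected sensitivity = 0.60 + 0.40 × 0.10 = 64%, or 9 extra cancers.
- PPV falls from 135/(135 + 214) = 39% to 144/(144 + 620) = 19%.

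For reagent specificity between 95% and 85%, the added false positives run from 4275 × 0.0475 = 203 to 4455 × 0.1425 = 635 (the latter with 45 cancers).

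**7. Precision available.** With one-way discordance d, the half-width of the 95% CI for the paired specificity difference is 1.96 × √(d(1 − d)/n). For d = 0.0475 to 0.1425 and n = 4275 to 4455 this is about 0.6 to 1.0 percentage points. For d = 0.095 and n = 4275 it is 0.9 points.

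**8. Reagent + AFP is different.** Here the reagent replaces ultrasound. Take 225 cancers and suppose AFP alone supplies 20 to 50 of the 60 sensitivity points. The random reagent then gains 225 × 0.40 × 0.10 = 9 cancers. It loses 225 × 0.40 × 0.90 = 81 down to 225 × 0.10 × 0.90 = 20. Discordance runs both ways, and the worthless reagent looks worse rather than better.

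**The case against.** The case against is substantial, and several stronger readings have to be given up.

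- **A reader might infer that false positives are never compared.** The protocol does not support this. Section 3.7.4 sets both combinations and AFP + US against the same clinical diagnosis, with specificity and PPV and their intervals. A loss of the size shown above would be visible side by side.
- **A reader might apply the 0.90 to reagent + AFP, the first comparison in 3.7.5.** Step 8 shows that it does not carry over. It belongs to reagent + AFP + US alone, and even there it depends on an unstated combination rule and an unstated prevalence.
- **A reader might infer that the protocol would declare overall superiority for screening.** It does not say so; 3.7.5 speaks of superiority in sensitivity. The background sentence is motivation for a new biomarker, not a hypothesis.
- **A worthless reagent would not pass unnoticed.** Sections 3.3.1 and 3.7.4 require its own sensitivity and specificity, which would come out near 10% and 90%.
- **Test mechanics and margins commonly belong in the SAP**, which is not shown.

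One part of the concern survives all of these. The protocol itself chooses the endpoint of the between-strategy comparisons and limits it to sensitivity. That is a stated choice rather than a detail left for later. Separate intervals are also a weaker substitute for the paired difference that the design already allows.

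**Conclusion.** The concern holds in a limited form. All formal comparisons with AFP + US in 3.7.5 are on sensitivity. Specificity is estimated per strategy but has no paired comparison, although the background asks for improvement in both.

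For reagent + AFP + US under an either-positive rule, the non-inferiority test is uninformative and superiority needs only about six extra cancers. The illustrative chance of a worthless reagent passing runs from under 0.02 to about 0.90 as cancers rise from 45 to 225 at 60% AFP + US sensitivity, and to 0.97 with 225 cancers at about 50%. These figures show how little the test constrains specificity; they do not predict the trial's result. For reagent + AFP, both properties can move in either direction, which is itself a reason to report both. The weakness lies in what the comparisons can show; it does not invalidate the sensitivity estimates.

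**What to change.** In 3.7.5, beside each sensitivity comparison, add the paired difference in specificity between the same combination and AFP + US among reference-negative subjects, with a 95% CI from a McNemar-type method. Require any statement of superior sensitivity to give the accompanying change in specificity. State the positivity rule for each combination, since the meaning of these comparisons depends on it.

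A pre-set largest acceptable loss of specificity, required jointly with the sensitivity result, is optional. It is a trade-off for the sponsor to justify, and the documents offer no basis for a particular value.

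The cost is wording in the protocol and SAP and a little more analysis. No extra subjects, samples or examinations are needed. The downside for the sponsor is a possibly less favourable headline if specificity falls.

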### 3.3.5 Judgment criteria for negative and positive result of test reagent

The test results of the test reagent are judged according to the positive value in the instructions for use:

When the HCCscan value is greater than 58, the sample is judged to be positive; when the HCCscan value is less than or equal to 58, the sample is judged to be negative.

For the examinations of "US+AFP", the negative result and positive result are determined according to the following criteria:

1) The results of "US+AFP" is positive if one of the following situations is met:

(1) Serum AFP  $> 400$  ng/mL, regardless of whether any nodule is detected by ultrasound examination;

(2) A nodule  $\geq 2$  cm is detected by ultrasound examination, regardless of AFP serum concentration;

(3) A nodule  $\geq 1$  cm but  $< 2$  cm is detected by ultrasound examination, and serum AFP  $\geq 200$  ng/mL

2) Results that do not meet the above criteria are recorded as "US+AFP" negative.

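### The sensitivity-only superiority and non-inferiority tests of test reagent + AFP + US against AFP + US compare a strategy with one of its own components, so under an either-positive rule a kit unrelated to cancer can pass them

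*Protocol*

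**What the plan says.** Protocol section 3.7.5 lists the sensitivity comparisons. The first is "the sensitivity superiority of test reagent + AFP to conventional method (AFP+US) for screening liver cancer", which also identifies the conventional method as AFP + US. The second is "the sensitivity superiority of test reagent + AFP + US to conventional method for screening liver cancer". The section then lists non-inferiority in sensitivity of the same triple combination, worded twice. It gives no margin, no named test and no accompanying requirement on specificity.

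Section 3.3.5 defines positivity for the reagent alone ("When the HCCscan value is greater than 58, the sample is judged to be positive") and for US+AFP through three criteria, with everything else negative. It gives no rule for the triple combination. Section 3.7.4 says to "compare the diagnostic performance of test reagent + AFP, test reagent + AFP + US, AFP + US to the clinical diagnostic criteria" and provides formulas for sensitivity, specificity and predictive values with 95% confidence intervals, but does not tie any of these to the conclusions of 3.7.5. Section 3.7.1 makes tests two-sided by default. Section 3.3.2 plans at least 4500 usable samples without saying how many cancers are expected.

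**The concern.** The tested strategy is the comparator plus one more test, and the endpoint is sensitivity alone. If a positive reagent result is enough to make the combination positive, adding the reagent can only move cancers from missed to detected. Sensitivity then rises for any reagent that is sometimes positive among the missed cancers, whether or not its result has anything to do with cancer. The price, extra false positives, falls entirely on specificity, which section 3.7.5 does not test.

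A positive result would be read as showing that the kit adds to current screening. The test as framed does not ask that question. It asks whether some missed cancers were reagent positive, and chance positives can answer yes. The non-inferiority version asks even less.

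**Working it through.** **Inputs from the protocol.** Two-sided tests (3.7.1). Alpha 0.05, inferred from the 95% intervals in 3.7.4. At least 4500 samples in the diagnostic part (3.3.2). The Background gives AFP sensitivity of about 60%, and ultrasound sensitivity of 84% for nodules above 2 cm and 33% for 0.5 to 2 cm. These are single-test figures, used here only to bracket the comparator.

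**Assumptions.** The combination is positive if the reagent or US+AFP is positive. The margin is zero. The test is exact McNemar. Comparator sensitivity S is 60% or 84%. The uninformative reagent is positive with probability f = 10% in everyone, independently of disease and of US+AFP. The number of cancers n is 45, 90, 150, 225 or 450, that is 1%, 2%, 3.3%, 5% or 10% of 4500.

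**The plan's own figure.** The 4500 cannot be reproduced, because no prevalence, sensitivity, margin, alpha or power is given for it.

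**Step 1: direction of discordance.** Under the either-positive rule no cancer is positive on US+AFP and negative on the combination, so one discordant cell is always empty.

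- Sensitivity of combination = S + (1 − S) × P(reagent positive | cancer missed by US+AFP).
- The difference is never negative, so non-inferiority is true for any margin.
- For the random reagent the difference is f(1 − S): 0.10 × 0.40 = 4.0 points at S = 60%, and 0.10 × 0.16 = 1.6 points at S = 84%.

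**Step 2: rejection threshold.** With b discordant cancers on one side and none on the other, the exact two-sided p is 2 × 0.5^b. For b = 5 this is 0.0625 and for b = 6 it is 0.031, so six are needed. The asymptotic test without continuity correction has chi-square equal to b and rejects at b = 4 (4 > 3.84).

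**Step 3: probability that the random reagent is declared superior.** P(X ≥ 6) with X ~ Binomial(n, f(1 − S)):

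| Cancers n | S = 60% | S = 84% |
|---|---|---|
| 45 | 0.9% | about 0% |
| 90 | 15% | 0.3% |
| 150 | 56% | 3% |
| 225 | 89% | 15% |
| 450 | about 100% | 73% |

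Sensitivity to the assumptions: at S = 60% and f = 5% the probability is 1.0% at 90 cancers and 8.2% at 150; at S = 60% and f = 20% it is 73.5% at 90. The uncorrected asymptotic test gives 49% instead of 15% at 90 cancers, S = 60%, f = 10%.

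**Step 4: what the test does not see.** The same reagent multiplies the specificity of US+AFP by 1 − f. From an illustrative 95%, it falls to 0.95 × 0.90 = 85.5% at f = 10%.

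**Step 5: the other comparison.** Test reagent + AFP does not contain ultrasound, so cancers can be discordant in either direction against AFP + US. The argument does not apply to it.

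**The case against.** The strongest reply is that neither the margin nor the either-positive rule is in the protocol, and both could sit in an analysis plan that is not shown. That stands: both are assumptions here. The existing US+AFP rule in 3.3.5 is itself graded, since a nodule of 1 cm to under 2 cm counts only with AFP of at least 200 ng/mL. A graded triple rule could raise sensitivity without being nested, and could make discordance two-sided. Under an all-positive rule sensitivity could not exceed that of US+AFP. A margin above zero would weaken the problem but not remove it: a random reagent that is positive often enough exceeds any margin below 1 − S, because sensitivity ignores false positives.

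A second reply is that the section compares sensitivity, and if the combination finds more cancers then rejecting equality is correct. That is also true. The test is not invalid for its literal hypothesis; the hypothesis is too weak for a claim of added value.

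Third, section 3.7.4 reports the reagent's own sensitivity and specificity, so a random kit would be exposed beside the claim. It would be visible, but nothing makes the claim depend on it.

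Two stronger readings are tempting. A reader might infer that the superiority null is false for every reagent that is ever positive. It is not: a reagent positive only in subjects without cancer, or only in cancers already detected by US+AFP, leaves the difference at exactly zero. A reader might also infer that the chance of a spurious claim is generally far above 5%. The table does not support that; it runs from about 0% to about 100%, and the protocol fixes none of the three quantities that decide it.

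**Conclusion.** The concern holds in conditional form. Section 3.7.5 commits to superiority and non-inferiority claims on sensitivity alone for a strategy that contains its comparator, with no specificity condition. Under an either-positive rule, non-inferiority is guaranteed. With a zero margin as well, a reagent independent of cancer makes the superiority null false whenever US+AFP misses some cancers. How often that turns into a declared success depends on prevalence, the reagent's positive rate and comparator sensitivity, all assumed here. It is negligible with few cancers or a sensitive comparator, and close to certain with several hundred cancers and a comparator near 60%. Because the defect rests on two unstated rules and the descriptive specificity results would be on view, this is something that should be fixed rather than a fatal flaw.

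**What to change.** In section 3.7.5, do not rest a superiority or non-inferiority claim for the triple combination on sensitivity alone. Instead:

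- Among subjects negative on US+AFP, test whether the reagent-positive rate is higher in reference-positive than in reference-negative subjects, for example with a two-sample score test, and give the ratio of the two rates with its 95% CI. An uninformative reagent then passes only at the nominal error rate. The ratio matters as well as the p-value, because with enough cases a barely informative reagent would also reach significance.
- Report the triple combination's gain in sensitivity together with its loss in specificity against US+AFP, each with a paired 95% CI.
- State the positivity rule for the triple combination, since both quantities depend on it.
- Leave the test of test reagent + AFP against AFP + US as it is.

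The change is to wording and should be made before unblinding; section 3.3.1 already has every subject undergo all the tests needed. The cost is that the claim becomes harder to obtain and rests on the smaller number of cancers that US+AFP misses.
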